15.3.4 Other Safety Data

Other safety data collected (e.g., ECG, vital signs) will be listed and summarized using descriptive statistics as appropriate. Notable values will be flagged. Notable/Abnormal values for safety data will be further specified in the RAP.

15.3.5 Immunological Analysis

Treatment in vivo with TKI drugs may increase the cytotoxic response in CML patients, helping them to control the disease progression in the absence of treatment. The analysis of the progression of these patients will allow us to correlate the cytotoxic response developed by previous treatment with different TKIs with a CML relapse in order to describe new biomarkers that may predict a successful treatment interruption in these patients.

15.3.5.1 Immunological Assays:

1. Phenotypic Assays: 6 samples per patient
 - a. Cell characterization: NK cells (CD3- CD56+; CD16+ CD56+; TNF α ; IFN α ; Granzyme b NK-LGL cells (CD56+ CD57+), T-LGL cells (CD3+ CD57+), CD8 TCR α / β , NK markers (NKG2D, KIR2DL2/DL3/DS2, KIR2DL5B).
 - b. Differentiation and maturation (NKG2A/CD16) and proliferation (NK67) markers of NK cells.
 - c. CD4+ T cells activation markers: CD25 CD69 HLA-DR.
 - d. Predictive markers of CML relapse: T regs (CD4+ CD25int-hi CD127low), CD8+ T cells (PD-1/PD-L1) and plasmacytoid dendritic cells (CD86+).

15.4 Secondary objectives

15.4.1 Secondary efficacy variables:

- To evaluate the Major Molecular Response (MMR) and Molecular Response (MR) rates at 3, 6, 12 months and at the End of Treatment (EoT) visit. Based on:
 - MMR is defined as \geq 3-log reduction in BCR-ABL transcripts or a ratio of $\leq 0.1\%$ on the International Scale (IS)
 - Molecular Response (MR): As defined in section 4. Definition of Terms
- Percentage of Participants Alive at Month 6, 12 at the EoT visit.
- Number of confirmed MR4 and MR4.5. [at end of treatment]

- The rate of confirmed MR4 and MR4.5 at the end of treatment.
- Number of Complete Cytogenetic Responses (CCyR) [Time Frame: After one year from study entry]
- The rate of Complete Cytogenetic Response (CCyR) at 1 year.
- Number of days to response (CCyR, MMR, MR4, MR4.5). [Time Frame: at the EoT visit]
- The median time to response and the overall estimated probability of response (CCyR, MMR, MR4, MR4.5).
- Number of overall surviving patients [Time Frame: at the EoT visit]
- Number of progression-free survival patients. [Time Frame: at the EoT visit]
- Number of failure-free survival patients. [Time Frame at the EoT visit]
- Number of event-free survival patients.[Time Frame: at the EoT visit]
- Immunological Studies

15.4.2 Analyses Methods for Secondary Objectives

A descriptive analysis of the secondary objectives will be carried out. Qualitative variables will be summarized by counts and percentages. Quantitative variables will be summarized by means of mean, standard deviation, minimum, maximum and main quartiles. The 95% confidence intervals will also be calculated.

The hypothesis of normality will be tested by the Shapiro-Wilk test. A repeated measurement ANOVA or its equivalent non-parametric test will be used depending on the result of this test. The qualitative variables will be analyzed by means of the Fisher Chi-square test/exact test or Cochran's Q test, as appropriate.

Survival analysis will be performed using the Kaplan-Meier estimation method and the Log-rank test. A p-value of <0.05 will be considered statistically significant.

15.5 Sample Size Calculation

There will be no formal calculation of the sample size. The sample size is selected to allow sufficient data collection for the DLT and safety assessment. It is an exploratory study. The minimum number of patients for the DLT evaluation will be 10 if no DLT is observed. After MTD is calculated, 26 more patients will be recruited for the dose variation phase. 36 patients (both, a first group of 10 patients and a second of 26 patients) will receive bosutinib 400 mg/day in monotherapy during one cycle of treatment. According to previous experience (*Tim H Brümmendorf et al, 2015; Jorge E. Cortes et al, 2018*), we assume that, at most, 15% of the patients included will not enter the dose escalation phase after the first month of treatment with bosutinib, due to side effects. Consequently, a total of 30-31 patients will receive the combination of bosutinib plus atezolizumab.

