8 STUDY OBJECTIVE

8.1 Primary Objective

The primary objective is to evaluate the safety profile of bosutinib 400mg/day in combination with atezolizumab as a first line treatment in participants with chronic phase-chronic myeloid leukemia.

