9 STUDY DESIGN

This is a phase Ib/II, two arms, open-label and dose-escalation study designed to determine the safety profile and the recommended phase III dose (RP3D) of bosutinib when administered in combination with atezolizumab in naïve patients with chronic myeloid leukemia in chronic phase. This study has two groups of patients (Figure 1).

[figure not shown]
[figure not shown]
[figure not shown]

Figure 1. Chronogram of the study

LAST 26 PATIENTS INCLUDED

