11 TREATMENT

11.1 Study Treatment

Study treatments: Bosutinib (400 mg/day orally)

Atezolizumab (840 mg q2wk or 1680 mg q4wk)

Study drugs: Bosutinib (Bosulif® 100 mg film-coated tablets, Pfizer S.L.U.)

Yellow oval (width: 5.6 mm; length: 10.7 mm) biconvex, film-coated tablet debossed with “Pfizer” on one side and “100” on the other side. Each tablet contains 100 mg bosutinib (as monohydrate).

Bosutinib (Bosulif® 400 mg film-coated tablets, Pfizer S.L.U.)

Orange oval (width: 8.8 mm; length: 16.9 mm) biconvex, film-coated tablet debossed with “Pfizer” on one side and “400” on the other side. Each tablet contains 400 mg bosutinib (as monohydrate).

Atezolizumab (Tecentriq 840 mg concentrate for solution for infusion, Roche Registration GmbH)

Bosutinib study drug will be provided by Pfizer Europe MA EEIG and Atezolizumab will be provided by Roche Registration GmbH.

Patients will receive bosutinib at 400 mg/day orally. Bosutinib will be self-administered by the patient on a daily schedule.

Atezolizumab should be given intravenously in the site. If the first infusion is tolerated (intravenously administration over 60 minutes), all subsequent infusions may be delivered over 30 minutes. Patients will receive atezolizumab 840 mg q2w or 1680 mg q4w. Each 28-days (4 weeks) is referred to as 1 cycle.

Study treatments will be provided only to eligible patients at qualified centers.

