11.6.1.2 Hematologic Treatment-Related Toxicity

Dose reductions are recommended for severe or persistent neutropenia and thrombocytopenia. The management of hematologic treatment-related toxicities is summarized in Table 2.

Table 2. Hematologic Treatment-Related Toxicity

Adverse Event	Action
Grade 1	Current dose level
Grade 2	Current dose level
Grade 3 ^a	Withhold treatment: If recovered to Grade ≤ 2 within 2 weeks of treatment hold: re-introduce study drug at same dose. If recovered within 4 weeks of treatment hold: reduce study drug by 1 dose level. At subsequent occurrences of Grade 3 toxicity, dose must be reduced upon recovery to Grade ≤ 2 . If recovery takes longer than 4 weeks, the Investigator should contact the Sponsor to determine if the patient may continue on treatment.
Grade 4 ^a	Withhold treatment. Investigator and Sponsor to review to determine if patient may continue on treatment with appropriate dose reduction. 
a. For patients requiring dose reduction due to toxicity, who have been free of the toxicity (Grade ≤ 1) for at least 1 month and are otherwise tolerating study drug, the Investigator may choose to re-escalate dose by 1 dose level back to starting dose

Subjects fulfilling criteria for dose escalation due to suboptimal response, but also exhibiting Grade 2 hematologic treatment related toxicity will be eligible for dose escalation; however, if hematologic toxicity increases to Grade 3 or 4 after dose escalation, the subject will be managed as per the instructions for Grade 3 or 4 hematological toxicities in Table 2.

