15 PLANNED STATISTICAL ANALYSIS

This is a phase Ib/II, single arm, open-label and dose-escalation study designed to determine the safety profile and the recommended phase III dose of bosutinib when administered in combination with atezolizumab in naïve patients with chronic myeloid leukemia in chronic phase.

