6.1. General features

Principal features of this analysis have been specified in the protocol according to ICH E3 ("Structure and content of clinical study reports") and ICH E9 ("Statistical Principles for Clinical Trials" and addendum Draft R1).

This is a phase Ib/II, single arm, open-label and dose-escalation study designed to determine the safety profile and the recommended phase III dose of bosutinib when administered in combination with atezolizumab in naïve patients with chronic myeloid leukemia in chronic phase.

The investigator should document and explain any deviation from the approved protocol. All significant protocol deviations will be recorded and reported in the Clinical Study Report.

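### The protocol and SAP promise an MTD and a bosutinib phase III dose from dose escalation, but the treatment plan has one planned bosutinib dose level and no MTD rule for either drug

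*Protocol*

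**What the plan says.** Several sections describe a dose-finding trial. Protocol Section 9 says the study is "designed to determine the safety profile and the recommended phase III dose (RP3D) of bosutinib when administered in combination with atezolizumab"; the synopsis and SAP 4.1 agree. Protocol Section 15 opens: "This is a phase Ib/II, single arm, open-label and dose-escalation study". SAP 6.1 uses the same label and gives the aim as "designed to determine the safety profile and the recommended phase III dose of bosutinib when administered in combination with atezolizumab". Protocol 15.5, repeated in SAP 4.3, then says: "After MTD is calculated, 26 more patients will be recruited for the dose variation phase". The synopsis has nearly the same sentence but calls the later stage dose escalation.

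The treatment sections describe something else. Protocol 11.1 states: "Patients will receive bosutinib at 400 mg/day orally". Sections 9.2 to 9.4 plan that dose for the monotherapy cycle, for the 12 combination cycles in both groups, and for the 12 closing cycles. Group 1 receives atezolizumab 840 mg every 2 weeks for 2 cycles, then 1680 mg every 4 weeks for 10. Group 2 receives 1680 mg every 4 weeks for 12 cycles. Under Section 9.1, Group 2 is enrolled if at least 9 of the first 10 patients have no DLT in the first two combination cycles; otherwise the trial ends. Under Section 9.3.2, DLTs in two or more patients at 1680 mg every 4 weeks move everyone to 840 mg every 2 weeks, which that section calls a reduction.

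The objectives do not mention dose finding. Section 8.1 reads: "The primary objective is to evaluate the safety profile of bosutinib 400mg/day in combination with atezolizumab as a first line treatment". Section 8.2 lists neither an MTD nor an RP3D.

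**The concern.** An MTD, or a phase III dose reached by escalation, needs at least two assigned dose levels, a definition of tolerable toxicity, and a rule that turns the DLT counts into a dose. None of these is visible here. If the labels stay, a clinical study report could present 400 mg/day as an MTD or as a recommended phase III dose of bosutinib found by escalation. In fact that dose was chosen beforehand and is the only one planned. The sequence in 15.5 also puts an MTD calculation before Group 2, whereas Section 9.1 opens Group 2 on a simple DLT count.

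**Working it through.** **1. The plan's own figure.** Protocol 15.5 expects 36 patients, at most 15% of whom do not reach the combination: 36 × (1 − 0.15) = 30.6. This matches the stated 30-31, so that arithmetic is not in question. There is no MTD, target DLT rate, alpha or power to reproduce.

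**2. Planned bosutinib dose levels (Protocol 9.2 to 9.4).** First therapy, 400 mg/day. Second therapy, 400 mg/day in both groups. Third therapy, 400 mg/day. That is one level, with no cohort at any other. Section 11.6.1 allows an individual patient to go to 300 mg, or to 200 mg with sponsor approval, for toxicity. Section 11.6.1.2 mentions "Subjects fulfilling criteria for dose escalation due to suboptimal response", but the documents give no such criteria and no level above 400 mg. Neither provision assigns patients to dose levels.

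**3. Could the MTD be that of atezolizumab?** Section 15.5 names no drug. Amount per 28-day cycle: 2 × 840 = 1680 mg on the two-weekly schedule, 1 × 1680 = 1680 mg on the four-weekly one. The amount per infusion doubles but the four-week total does not change. Only the two-weekly schedule is assessed before the 26 patients are recruited.

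**4. What the DLT rules do.** In Group 1, two or more patients with a DLT end the trial. At 1680 mg every 4 weeks, two or more change the atezolizumab schedule. Neither rule leads to another bosutinib dose.

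**5. Analysis.** Protocol Section 15 and SAP 6.4, 6.5 and 6.9 contain no MTD definition, estimator or RP3D analysis. SAP 4.4 plans no interim analysis, although 4.3 places an MTD calculation before Group 2.

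**6. What the 10-patient check can show.** With true DLT rate p and n evaluable patients, P(continue) = (1 − p)^n + n·p·(1 − p)^(n − 1). The documents give no p, so these rates are assumptions. Columns n = 9 and n = 8 apply if 15% of the first 10 are lost after cycle 1 (10 × 0.85 = 8.5) and are not replaced.

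| Assumed p | n = 10 | n = 9 | n = 8 |
|---|---|---|---|
| 5% | 0.914 | 0.929 | 0.943 |
| 10% | 0.736 | 0.775 | 0.813 |
| 20% | 0.376 | 0.436 | 0.503 |
| 30% | 0.149 | 0.196 | 0.255 |
| 40% | 0.046 | 0.071 | 0.106 |

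**7. Precision after a pass (exact binomial, 95%).** 0/10: 0 to 30.8%. 1/10: 0.3% to 44.5%. With fewer evaluable patients, the upper limit is 33.6% for 0/9 and 36.9% for 0/8. For an event not seen in 30 combination patients, the upper limit is 1 − 0.025^(1/30) = 11.6%.

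**8. A second mismatch.** Section 15.5 makes 10 the minimum for DLT evaluation on condition that no DLT is seen, which implies more patients if one occurs. Under Section 9.1, one DLT in 10 still opens Group 2, with nobody added.

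**The case against.** Four points can fairly be made for the plan.

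- **The sample size does not rest on the MTD.** A reader might infer that 10 + 26 has lost its basis. It has not. Protocol 15.5 says there is no formal calculation, and that the number was chosen to yield enough DLT and safety data in an exploratory study. The MTD sentence concerns when the 26 are recruited, and the 30-31 figure depends only on the 15% loss. This objection stands in full.
- **Bosutinib is not immovable.** A reader might infer that every patient stays at 400 mg. Section 11.6.1 allows individual reductions and re-escalation, so 400 mg/day is the planned dose only. This stands, but toxicity-driven changes in single patients do not make a dose comparison.
- **There is a planned step in atezolizumab.** The amount per infusion goes from 840 to 1680 mg, and Section 9.3.2 reverses this on DLTs. So it would be wrong to say that nothing is varied. What remains is that the 28-day totals are equal and that no rule converts the DLT counts into an MTD.
- **No planned estimate depends on the labels.** The listed objectives and SAP analyses include no MTD or RP3D, and SAP 6.5 already specifies exact binomial intervals for adverse events. This limits the harm to what the report may claim. The intervals above do not measure the wording defect; they show what a pass would support.

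**Conclusion.** The design cannot deliver an MTD for either drug, or an RP3D of bosutinib chosen by escalation. There is one planned bosutinib level, two atezolizumab schedules with the same 28-day total, and no target rate or decision rule. The stated aim and the MTD step placed before Group 2 are therefore wrong as written. The condition attached to the minimum of 10 also disagrees with Section 9.1.

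The documents do not support the further inference that the trial fails its primary objective. Safety of the combination at planned bosutinib 400 mg/day can be described as intended. The first 10 patients provide a go/stop check that continues with probability 0.736, 0.376 and 0.149 at assumed DLT rates of 10%, 20% and 30%. These figures assume 10 evaluable, independent patients with a common DLT rate. The dose-level count comes directly from Sections 9.2 to 9.4 and needs no assumption.

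**What to change.** Reconcile the synopsis, Protocol 9, 15 and 15.5, and SAP 4.1, 4.3 and 6.1 with the treatment plan in Protocol 9.2 to 9.4. Two routes are open to the sponsor:

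1. Specify the missing elements: dose levels, target DLT rate, MTD rule and the analysis that yields the RP3D.
2. Otherwise, remove the wording on dose escalation, the calculated MTD, the dose variation or escalation phase, and the RP3D of bosutinib. Describe a 10-patient DLT check followed by expansion, and report no MTD or RP3D.

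Under either route:

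- Bring the minimum-of-10 condition in 15.5 into line with Section 9.1.
- Reconcile Section 9.3.2, where a schedule with the same 28-day total is called a reduction, and Section 11.6.1.2, which refers to escalation criteria that are not given.
- State whether Group 1 patients lost before the combination are replaced, so that 10 are evaluable.
- Add the expected precision to the sample-size text: 0 to 30.8% for 0/10, 0.3 to 44.5% for 1/10, and an upper limit of 11.6% for 0/30.

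The second route needs wording changes only, and its price is a less ambitious stated aim. The first would be a change of design. No dose or clinical rule is proposed here.

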16 QUALITY CONTROL AND QUALITY ASSURANCE

The sponsor/CRO has implemented and maintains a quality assurance system with written SOPs to ensure that the trial is conducted and data are generated, documented and reported in compliance with the protocol, GCP and the applicable regulatory requirements.

The sponsor performs quality control and assurance checks on all clinical studies that it sponsored. Before enrolling any patients into this study, the sponsor or its designee, as well as the investigator, will review the protocol, the Clinical Investigator's Brochure; the eCRF model and the instructions for its completion; the procedure for obtaining informed consent; and the procedure for reporting AEs. A qualified representative of the sponsor will monitor the conduct of the study by both visiting the site and contacting it by telephone or email. During the visits, information recorded in the eCRFs will be verified against source documents. The sponsor's medical monitor will review the data for safety information. The sponsor's clinical research associates (CRAs) will review the data for legibility, completeness, and logical consistency. Additionally, the sponsor's CRAs and quality control staff will identify missing data, selected protocol violations, out-of-range data, and other data inconsistencies. Requests for data clarification or correction will be added to the electronic database and reviewed by the investigational site for resolution. The sponsor may visit the investigational site and perform a quality check of the eCRFs against source documents.

16.1 Investigators and Study Administrative Structure

The investigator must provide the sponsor with the following documents before enrolling any patient:

- A clinical trial agreement
- Documentation of financial disclosure
- Principal investigator's *curriculum vitae*

If any investigator retires, relocates, or otherwise withdraws from conducting the study, the responsibility for maintaining records shall be transferred to another person (e.g., sponsor, IRB/IEC, or other investigators) who accepts the responsibility. The sponsor must be notified in writing and agree to the change in advance.

16.2 Study Monitoring

This study will be monitored by representatives of the sponsor. Site visits will be made before the study begins, at regular intervals during the study, and at the study closeout. Communication by telephone, mail, and e-mail may be used, as needed, to supplement site visits. The investigator and the rest of the investigational team will cooperate with the sponsor, provide all appropriate documentation, and be available to discuss the study. Adequate time and space for these visits should be established in agreement with the investigator. The purpose of the site visits is to verify:

- Adherence to the protocol (the investigator should document and explain any deviation from the approved protocol)
- The completeness and accuracy of the data registered in the eCRFs and the dispensing and inventory records of the study medication and other study supplies
- Compliance with regulations
- These verifications will require comparison of the source documents to the eCRFs
- The scope, frequency and relevant details regarding the study monitoring will be detailed in the monitoring plan

17 ETHICAL CONDUCT OF THE STUDY

This study will be conducted in accordance with the ethical standards that have their origin in the Declaration of Helsinki and that are consistent with GCP guidelines and the applicable regulatory requirements.

17.1 Institutional Review Board or Ethics Committee Approval

The protocol and the ICF must have the approval of an IRB/IEC. The signed IRB/IEC approval letter must identify the documents approved (e.g., list the investigator's name, the protocol number and title, the date of the protocol and informed consent document, and the date of approval of the protocol and the informed consent document). Any advertisements used to recruit patients should also be reviewed by the IRB/IEC. The sponsor will not ship clinical supplies until a signed approval letter from the IRB/IEC has been received and a Clinical Trial Agreement has been signed by the sponsor and the clinical site.

17.2 Patient Information and Consent

Regulatory agencies have issued regulations to provide protection for human patients in clinical investigations and to describe the general requirements for informed consent.

A copy of the study ICF should be submitted to the sponsor for review and comment before its submission to the IRB/IEC. The study should not begin until the ICF has been reviewed and approved by the sponsor, and must not begin until the document has been approved by the IRB/IEC.

The ICF shall contain all the elements of the informed consent specified in the regulations. Some regulations may require the disclosure of additional information to the patient and/or inclusion of additional information in an informed consent document.

Nothing in this protocol or the regulations is intended to limit the authority of a physician to provide emergency medical care under applicable regulations. In addition, the investigator should be aware that some regulations require that he/she permits regulatory agencies to conduct inspections and review records pertaining to this clinical investigation.

17.3 Patient Confidentiality

The investigator must ensure anonymity of the patients; patients must not be identified by their names in any documents submitted to sponsor. Signed informed consent forms and identification patient enrollment log must be kept strictly confidential while allowing patient identification at the site.

17.4 Publication of the Study Protocol and Results

The sponsor ensures that the key design elements of this protocol will be posted in REec and any other publicly accessible database such as clinicaltrials.gov, if necessary in addition, upon study completion and finalization of the study report, the results of this study will be either submitted for publication and/or posted in REec and other public accessible database of clinical study results.

In addition, the sponsor may also publish the results in conferences and medical journals when deemed appropriate.

